10.2.3 Safety Analyses

All safety analyses will be performed on the Safety Population.

Endpoint	Statistical Analysis Methods

The Safety and tolerability objective (whether for Phase 2 or Phase 3) will be measured by the incidence of adverse events (AEs), serious adverse events (SAEs), adverse events leading to discontinuation, deaths, and laboratory abnormalities in each arm.
	
 Safety analyses will be performed in all treated participants. Descriptive statistics of safety will be presented using National Cancer Institute (NCI) Common Terminology Criteria for Adverse Events (CTCAE) version 5.0 by treatment group. All on-study AEs, treatment-related AEs, SAEs, and treatment-related SAEs will be tabulated using worst grade per NCI CTCAE v 5.0 criteria by system organ class and preferred term. On-study lab parameters including hematology, chemistry, liver function, and renal function will be summarized using worst grade NCI CTCAE v 5.0 criteria.

10.2.4 Other Analyses

PK and biomarker exploratory analyses will be described in the SAP finalized before database lock.

10.2.4.1 Pharmacokinetic Analyses

Trough concentrations of relatlimab will be plotted versus study day and cycle. Nivolumab end-of-infusion and trough (C_{trough}) concentrations will be tabulated using summary statistics. These data may also be pooled with other datasets for population PK analysis which will be presented in a separate report.

10.2.4.2 Immunogenicity Analyses

A listing will be provided for all available immunogenicity data. Baseline ADA positive subject is defined as a subject with positive seroconversion detected in the last sample before initiation of treatment. ADA-positive subject is a subject with at least one ADA-positive sample relative to baseline after initiation of the treatment. For each drug, frequency distribution of baseline ADA positive subjects and ADA positive subjects after initiation of the treatment will be summarized. To examine the potential relationship between immunogenicity and safety, a table summarizing

the frequency and type of AEs of special interest may be explored by immunogenicity status. In addition, potential relationships between immunogenicity and efficacy and/or PK may also be explored.

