#### 4.3.3.2 ADA Status of a Subject

- Baseline ADA-Positive Subject: A subject with baseline ADA-positive sample
- ADA-Positive Subject: A subject with at least one ADA-positive sample at any time after initiation of treatment
- *Persistent Positive (PP)*: ADA-positive sample at 2 or more consecutive timepoints where the first and last ADA-positive samples are at least 16 weeks apart

*Not PP - Last Sample Positive*: Not persistent positive with ADA-positive sample in the last sampling timepoint

- *Other Positive*: Not persistent positive but some ADA-positive samples with the last sampling being negative

*Neutralizing Positive*: At least one ADA-positive sample with neutralizing antibodies detected

- ADA-Negative Subject: A subject with no ADA-positive sample after the initiation of treatment

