#### **Clinical Implications:**

Clinical implications of positive ADA may be explored by a comparison of ADA-positive participants to ADA-negative participants.

Effect of immunogenicity on clearance of study drugs may be explored by comparison of clearance estimates (determined by PPK analysis), if appropriate. Effect of immunogenicity on safety will be explored by examining the frequency and type of AEs of special interest such as hypersensitivity/infusion reaction. Summary tables for incidence of each preferred terms and overall as a category of AEs will be provided, if the number of participants is of sufficient size (e.g., at least 10 participants). Otherwise, individual participant's safety profile will be examined and described based on a listing. Association between trough concentrations of study drugs and ADA assessments may be explored, as needed.

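### AEs of special interest are explored by ever-positive ADA status, with no rule on whether the AE came before or after the first positive sample and no exposure adjustment

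*Protocol*

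**What the plan says.** SAP 4.3.3.2 defines an ADA-positive subject as "A subject with at least one ADA-positive sample at any time after initiation of treatment". Protocol 10.2.4.2 and SAP Appendix 3 use the same rule, with no landmark or time window.

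On safety, Protocol 10.2.4.2 says that "the frequency and type of AEs of special interest may be explored by immunogenicity status". SAP 7.6.22 (Clinical Implications) is firmer: "Effect of immunogenicity on safety will be explored by examining the frequency and type of AEs of special interest such as hypersensitivity/infusion reaction". It names the groups: "Clinical implications of positive ADA may be explored by a comparison of ADA-positive participants to ADA-negative participants". Incidence tables by preferred term are promised if numbers suffice (10 participants is the example given); otherwise individual profiles are described from a listing.

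By default (SAP 7.1.1 and 6.1), AE tables count each subject once per preferred term and include events from first dose onward. SAP 7.6.22 does not change this for the ADA table. Exposure-adjusted rates appear in SAP 7.6.12, for all AEs, not by ADA status.

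On efficacy, Protocol 10.2.4.2 says only that "potential relationships between immunogenicity and efficacy and/or PK may also be explored". SAP 7.6.22 gives no method for it.

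**The concern.** ADA status is fixed by data collected after treatment starts, sometimes long after the AE it is meant to explain. Two problems follow.

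The first is time order. An AE can be tabulated under ADA-positive although the only positive sample came later.

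The second is unequal opportunity. More doses bring more ADA samples, more infusions and more time in which an AE can occur. A crude incidence comparison can then differ between the groups when ADA has no effect.

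SAP Appendix 3 itself stresses the importance of examining associations between ADA and clinical sequelae. A table that does not show which came first answers that question poorly.

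**Working it through.** The documents give no sample size, power or effect for this analysis, so there is no plan figure to reproduce.

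**Time order.** Protocol Table 9.5.1-1 schedules ADA samples predose at Cycles 1, 2 and 6, then at every 4th dose, then at Follow-Up Visits 1 and 2. The first post-baseline sample is therefore Cycle 2 Day 1 or, for someone who stops after one dose, Follow-Up Visit 1. Every first-infusion reaction comes before it. This follows from the schedule and needs no assumption.

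**Sampling opportunity.** Post-baseline samples for a participant who has stopped and completed both follow-up visits:
- 1 dose: 0 on treatment + 2 = 2
- 10 doses: Cycles 2, 6, 10 + 2 = 5
- 26 doses: Cycles 2, 6, 10, 14, 18, 22, 26 + 2 = 9

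P(ever positive) = 1 − (1 − p)^k, for k samples each positive with probability p. The documents give no p. At an assumed 5%:
- 1 − 0.95^2 = 9.8%
- 1 − 0.95^5 = 22.6%
- 1 − 0.95^9 = 37.0%

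**Simulation with no true ADA effect** (40,000 participants per scenario). From the documents: the sampling schedule, and the combination-arm PFS assumptions of median 11.8 months and 40% event-free (Protocol 10.1). Assumed: an exponential-mixture PFS model; cut-off uniform at about 7 to 27 months; 1% per month toxicity stops; p of 2%, 5% or 10%; AE rate either constant at 3% per month, or 10% per month decaying with a 90-day time constant; Follow-Up Visit 2 detecting ADA either equally well or 3 times better.

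| Detection | Median months on treatment, ever vs never positive | AE risk ratio, constant rate | AE risk ratio, early AEs | First AEs before first positive sample, ever-positive group |
|---|---|---|---|---|
| Equal at all samples | 10.0–10.6 vs 7.2–7.8 | 1.21–1.28 | 1.07–1.09 | 52–57% (constant), 77–81% (early) |
| Follow-Up Visit 2 three times better | 8.0–8.3 vs 7.9–8.0 | 1.05–1.09 | 0.97–1.02 | 59–62% (constant), 82–84% (early) |

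These runs put no upper limit on ADA sampling. SAP 4.3.1 mentions up to 12 cycles for PK measurements. If that limit also applied to ADA, the AE risk ratio would be 0.88–1.09 and the pre-positive share 45–80%.

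**Efficacy, if it were explored.** In the same runs, the PFS hazard ratio for ever versus never positive is 0.74–0.75 with equal detection and 1.05–1.11 with better Follow-Up Visit 2 detection. With ADA as a time-dependent covariate it is 0.94–1.04 and 1.00–1.07.

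**The case against.** The strongest reply has four parts.

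**Low stakes.** The formal immunogenicity endpoint is ADA incidence (Protocol Table 4-1), which is unaffected, and the AE table carries no test. For the AE type that the SAP names, the distortion may be under one participant. About 350 combination participants at the 5.9% reaction rate in Protocol 5.5.1 (a different regimen) give 20.65 reactors. At the simulated ADA incidence of 7.6–33.4% with equal detection, 1.6 to 6.9 would be ever-positive. A ratio of 1.09 adds at most 6.9 × 0.09 = 0.6 of a participant. This stands and limits the priority, although it does not settle the time order of those few cases.

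**The imbalance is not certain.** A reader might infer that longer-treated participants must fill the positive group, so that the table will show an association. The documents do not support that. Early stoppers are sampled about 30 and 100 days after the last dose, and SAP Appendix 3 says ADA is detected more reliably at low drug concentration. That could cancel the imbalance.

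**First positive sample is not ADA onset.** No sample is scheduled between Cycle 2 and Cycle 6, a gap of 16 weeks, and ADA-positive includes a 4-fold boost over a positive baseline. Antibody may be present before it is detected. Grade 3 or 4 infusion reactions lead to permanent discontinuation (Protocol Table 7.4-1). A reaction at Cycles 3 to 5 that stops treatment would therefore be followed by its next scheduled sample at Follow-Up Visit 1. Counting ADA-positive time only from the first positive sample would place that reaction in ADA-negative time unless Cycle 2 was already positive. This stands. The time-ordered analysis should be added, with a sensitivity rule, and should not replace the ever/never table.

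**Existing safeguards.** All ADA samples are listed with flags, by-subject AE listings are provided, and persistent and neutralizing categories are reported separately. These let a reader check individual cases but do not correct the comparison.

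**Conclusion.** The point holds for the AE exploration. The comparison in SAP 7.6.22 has no time order and no exposure adjustment, and first-infusion reactions can be counted under ADA-positive status acquired later. With no true effect, the risk ratio can be about 1.07–1.28 under equal detection and about 1 if off-drug samples detect better. In both settings, 52–84% of first AEs in the ever-positive group precede the first positive sample. The ratios and shares rest on assumed positivity, AE and discontinuation rates and are not estimates for this trial; the first-infusion ordering rests on the schedule alone.

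Two stronger readings are tempting. One is that a biased efficacy comparison is planned. The documents only leave that option open and specify no method. The other is that the AE table suffers immortal-time bias. In the strict sense that term fits a PFS, OS or response comparison; for AEs the problem is misattribution in time plus unequal sampling and exposure.

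The PFS, OS and ORR tests and ADA incidence are not affected. This is a cheap improvement to an exploratory analysis.

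**What to change.** In SAP 7.6.22, with a matching sentence in Protocol 10.2.4.2:

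1. Keep the ever/never table and label it descriptive.
2. Add these AEs by onset before versus after the first ADA-positive sample.
3. Add exposure-adjusted rates by time-dependent ADA status, with time before the first positive sample counted as ADA-negative. Present them within intervals since first dose, as SAP 7.6.12 does for all AEs. Otherwise early-clustering AEs fall mainly in ADA-negative time.
4. Add a sensitivity analysis that starts ADA-positive time at the last negative sample before the first positive one (the baseline sample if there is no later one). Reactions in a sampling gap, or leading to discontinuation before the next sample, are then not lost to ADA-negative time.
5. If efficacy by ADA is explored at all, use a landmark or a time-dependent ADA covariate.

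The cost is a few sentences and modest programming, since ADA sample dates, AE onset dates and exposure are already collected. The downside is that ADA onset is known only to within the sampling interval. Items 3 and 4 should be read as a late and an early bound on it.

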10.2.4.3 Outcomes Research

Analyses of EQ-5D-3L, FACT-M (and GP5 item alone), and WPAI:GH scores will be performed in all randomized participants who have an assessment at baseline (Day 1, assessment prior to administration of drug on day of first dose) and at least 1 subsequent assessment while on treatment. Questionnaire completion rate, defined as the proportion of questionnaires actually received out of the expected number, will be calculated and summarized at each assessment point.

EQ-5D-3L data collected during on-study clinic visits, at Follow-up Visits 1 and 2, and during the survival follow-up phase, will be described by treatment group as randomized in the following ways:

- EQ-5D-3L index scores and post-baseline changes in scores will be summarized at each assessment time point using descriptive statistics (ie, N, mean with SD and 95% CI, median, first and third quartiles, minimum, maximum). In the base case, scores will be calculated using the UK preference-weighting algorithm.
- EQ-5D-3L VAS scores and post-baseline changes in scores will be summarized at each assessment time point using descriptive statistics (ie, N, mean with SD and 95% CI, median, first and third quartiles, minimum, maximum).
- The proportion (N) of participants reporting no, moderate, or extreme problems will be presented for each of the 5 EQ-5D-3L dimensions at each assessment time point.
- A by-participant listing of the level of problems in each dimension, corresponding EQ-5D-3L health state (ie, 5-digit vector), EQ-5D-3L index score, and EQ-5D-3L VAS score will be provided.

FACT-M data collected during on-study clinic visits, at Follow-up Visits 1 and 2, and during the survival follow-up phase will be described by treatment group as randomized in the following ways:

- Scores and post-baseline changes in scores for the FACT-M total scale and subscales, and the GP5 will be summarized at each assessment time point using descriptive statistics (ie, N, mean with SD and 95% CI, median, first and third quartiles, minimum, maximum, and frequency of responses for GP5 item).
- The proportion (N) of participants with symptomatic deterioration, defined as a clinically meaningful decline in FACT-M MS score (worsening from baseline ≥ 34 points) or death, will be summarized at each assessment time point (on-study visits only).

WPAI:GH data collected at baseline, on-treatment visits, and at follow-up Visits 1 and 2 will be described by treatment group as randomized in the following ways:

- Employment status (Q1, Yes/No) will be summarized at each assessment time point using frequency counts and percentages.

- Hours actually worked during the past 7 days (Q4) will be summarized at each assessment time point as a categorical variable (> 0 hour/0 hour) using frequency counts and percentages.
- Absenteeism, presenteeism, work productivity loss, and activity impairment scores and post-baseline changes in scores will be summarized at each assessment time point using descriptive statistics (ie, N, mean with SD and 95% CI, median, first and third quartiles, minimum, maximum). Absenteeism and work productivity loss scores will be summarized for participants who were employed (Q1=Yes). Presenteeism will be summarized for participants who actually worked during the past 7 days (Q4 > 0 hour). Activity impairment will be summarized for all participants.

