9.1.3.2 FACT-M

The FACT-M questionnaire will be used to assess the effects of disease symptoms on functioning and well-being. As a generic cancer-related core, the FACT-M includes the 27-item FACT General (FACT-G) to assess physical well-being (PWB; seven items), social/family well-being (SWB; seven items), emotional well-being (EWB; six items), and functional well-being (FWB; seven items). In addition, the FACT-M includes a 16-item disease-specific Melanoma Subscale (MS). A single item from the FACT-M (ie, GP5) will be used to assess the extent of perceived bother due

to symptomatic AEs. Evidence exists for the validity of this item and its usefulness as an overall summary measure of burden due to symptomatic treatment toxicities.³³

Each FACT-M item is rated on a 5-point scale ranging from 0 (not at all) to 4 (very much). Scores for the PWB, FWB, SWB, and EWB subscales can be combined to produce a FACT-G total score, which provides an overall indicant of generic quality of life, while the FACT-G and MS scores can be combined to produce a total score for the FACT-M, which provides a composite measure of general and targeted quality of life.

A variant of the total score that is often more sensitive to physical and functional outcomes, the Trial Outcome Index (TOI), can be derived by summing the PWB, FWB, and MS scores. All scores are scaled so that higher values indicate better functioning as well as lower symptom burden.

For any given scale, the minimally important difference (MID) represents the smallest difference in score that informed patients might perceive as important and that would warrant consideration of a change in management. With regard to the MS, the minimally important difference has been estimated as a change of 2-4 points.³⁴ For this trial, we will use the midpoint of the range (ie, a change ≥ 3 points) to define a minimally important change in MS score. This interpretation has been applied in previous investigations.³⁵

The FACT-M uses a 7-day recall period.

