#### **4.3.4.2 FACT-M**

The FACT-M questionnaire will be used to assess the effects of disease symptoms on functioning and well-being. The FACT-M includes the 27-items from the FACT General (FACT-G) to assess physical well-being (PWB; seven items), social/family well-being (SWB; seven items), emotional well-being (EWB; six items), and functional well-being (FWB; seven items). In addition, the FACT-M includes a 16-item disease-specific melanoma subscale (MS) and an 8-item melanoma surgery scale (MSS). The GP5 item, which will also be analyzed on its own is: "I am bothered by side effects of treatment".

Each FACT-M item is rated on a 5-point scale ranging from 0 (not at all) to 4 (very much). Scores for the PWB, FWB, SWB, and EWB subscales can be combined to produce a FACT-G total score, which provides an overall indicant of generic quality of life, while the FACT-G and MS scores can be combined to produce a total score for the FACT-M, which provides a composite measure of general and targeted quality of life.

A variant of the total score that is often more sensitive to physical and functional outcomes, the Trial Outcome Index, can be derived by summing the PWB, FWB, and MS scores. All scores are scaled so that higher values indicate better functioning as well as lower symptom burden.

For any given scale, the minimally important difference represents the smallest difference in score that informed patients might perceive as important and that would warrant consideration of a change in management. With regard to the MS, the minimally important difference has been estimated as a change of 2-4 points. For this trial, we will use the midpoint of the range (i.e., a change  $\geq 3$  points) to define a minimally important change in MS score. This interpretation has been applied in previous investigations.

Data will be scored according to the algorithm described in the FACT-M scoring manual.

If there are missing items, subscale scores can be prorated. This can be done using the following formula:

$$\text{Prorated subscale score} = [\text{Sum of item scores}] \times [\text{N of items in subscale}] \div [\text{N of items answered}]$$

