### **7.9.3 Time to Meaningful Symptomatic Deterioration of FACT-M MS**

The time to meaningful symptomatic deterioration is defined as the time (in months) between the date of randomization and the first date of a 3-point or more decrease from baseline in FACT-M Melanoma Subscale (MS). The focus of this analysis is the period while patients remain on treatment; subjects who did not meet the criteria of a 3-point or more increase from baseline in FACT-M MS will be censored on the date of their last FACT-M assessment. Patients without any PRO measurement are censored at randomization.

Time to meaningful symptomatic deterioration will be analyzed using a Cox proportional hazards model with baseline as a covariate. The estimate of the hazard ratio along with a two-sided 95% CI for the hazard ratio will be calculated.

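### Protocol 10.2.4.3 sets symptomatic deterioration at a fall of 34 points on the 0-64 FACT-M Melanoma Subscale, contradicting the trial's own 3-point criterion

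*Protocol*

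**What the plan says.** Protocol 10.2.4.3 (Outcomes Research) lists, among the FACT-M summaries, the proportion with symptomatic deterioration, "defined as a clinically meaningful decline in FACT-M MS score (worsening from baseline ≥ 34 points) or death". It is to be reported at each on-study visit, in randomized participants with a baseline and at least one later on-treatment assessment.

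Protocol 9.1.3.2 gives the basis for a meaningful change on this subscale: "the minimally important difference has been estimated as a change of 2-4 points". It then says "we will use the midpoint of the range (ie, a change ≥ 3 points) to define a minimally important change in MS score". SAP 4.3.4.2 adopts the same rule: "For this trial, we will use the midpoint of the range", again 3 points or more. SAP 7.9.3 defines time to meaningful symptomatic deterioration from randomization to the "first date of a 3-point or more decrease from baseline in FACT-M Melanoma Subscale (MS").

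On direction, Protocol 9.1.3.2 says "All scores are scaled so that higher values indicate better functioning as well as lower symptom burden", so deterioration is a decrease. SAP 7.9.3 nevertheless censors those who did not have an increase of 3 points or more.

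SAP 7.9.2, the FACT-M section, lists completion rates, mean scores and changes, and response frequencies for the GP5 item. It does not list the deterioration proportion.

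**The concern.** Three places in the two documents set the meaningful MS change at 3 points. The one place that specifies a responder proportion sets it at 34 and calls that clinically meaningful. Both figures cannot describe the same concept on the same subscale.

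The threshold decides who is counted as having deteriorated. Because SAP 7.9.2 does not carry the analysis, Protocol 10.2.4.3 is its only specification. Someone implementing the protocol would either use 34 points or leave the output out without any recorded decision. In the first case the symptom component would register almost no one. In the second, a protocol-specified summary would disappear unexplained.

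The increase/decrease slip in SAP 7.9.3 concerns the same measure and is best corrected at the same time. Read literally, a participant whose score falls by 3 points and never rises by 3 has an event under one sentence and is censored under the next.

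**Working it through.** **Inputs from the documents.** Protocol 9.1.3.2 gives 16 MS items, each scored 0 to 4, higher scores better, and a minimally important difference of 2-4 points. Protocol 10.2.4.3 gives the threshold of 34.

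**Reproducing the trial's own criterion.** The midpoint of 2-4 is (2 + 4)/2 = 3. This matches Protocol 9.1.3.2, SAP 4.3.4.2 and SAP 7.9.3. No point in the range gives 34: the low end is 2, the midpoint 3 and the high end 4.

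**Size of 34 on this scale.**
- Range: 16 × 4 = 64, so scores run from 0 to 64.
- Share of the scale: 34/64 = 53%, against 3/64 = 4.7% for the stated criterion.
- Ratio to the stated criterion: 34/3 = 11.3. Ratio to the top of the 2-4 range: 34/4 = 8.5.
- Average fall per item: 34/16 = 2.1 categories on every one of the 16 items, against 3/16 = 0.19.
- Floor: the score cannot go below 0, so a baseline below 34 rules out a fall of 34.

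**Consequence if applied literally.** The documents give neither the mean nor the SD of MS change, so both are assumed and varied. With change approximately normal, mean μ and SD σ, and a continuity correction for whole-number scores:

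P(fall ≥ t) = Φ((−(t − 0.5) − μ)/σ)

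For example, with μ = −6 and σ = 15, P(fall ≥ 34) = Φ((−33.5 + 6)/15) = Φ(−1.83) = 3.3%. With μ = 0 and σ = 6, P(fall ≥ 3) = Φ(−2.5/6) = Φ(−0.42) = 34%.

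| Assumed mean change | Assumed SD | P(fall ≥ 34) | P(fall ≥ 3) |
|---|---|---|---|
| 0 | 6 | <0.01% | 33.8% |
| 0 | 10 | 0.04% | 40.1% |
| 0 | 15 | 1.3% | 43.4% |
| −3 | 6 | <0.01% | 53.3% |
| −3 | 10 | 0.11% | 52.0% |
| −3 | 15 | 2.1% | 51.3% |
| −6 | 6 | <0.01% | 72.0% |
| −6 | 10 | 0.30% | 63.7% |
| −6 | 15 | 3.3% | 59.2% |

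Over this grid the 34-point criterion is met by about 0-3% of assessed participants at a visit, and the 3-point criterion by 34-72%. The approximation ignores the scale's floor, which excludes anyone with a baseline below 34 from the 34-point event altogether.

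**The case against.** The best case against has four parts.

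*It is a slip that nobody would program.* The SAP uses 3 points wherever it sets an MS threshold, omits the proportion, and in section 9 ties report content to the analyses it describes. The 34 may be a mistyped 3, a 3-4 that lost its hyphen, or a stray citation number, since reference 34 is the source of the 2-4 range. A fault in reading the PDF cannot be ruled out either. This supports checking the original page and keeping the point in proportion. It does not remove the point: the protocol text as read is wrong, and the SAP neither corrects the figure nor says the analysis was dropped.

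*It is exploratory.* This stands. The only endpoint listed for the symptom-burden objective is time to deterioration, which uses 3 points. The proportion is a descriptive bullet, and nothing beyond PFS, OS and ORR is formally tested.

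*The percentages rest on assumptions.* This also stands, which is why a range is shown. The contradiction and the scale arithmetic need no assumptions.

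*The treatment of death.* Because the proportion counts death, a reader might infer that at 34 points it becomes in effect a death rate. The documents do not support going that far: they give no SD of change and no expected number of deaths among the participants and visits in this summary. A reader might also infer that SAP 7.9.3 should count death because Protocol 10.2.4.3 does. Protocol Table 4-1 defines time to deterioration by the MS alone, and SAP 7.9.3 focuses on the on-treatment period. A symptom-only time to event and a symptom-or-death proportion are different estimands, not a contradiction.

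**Conclusion.** The inconsistency is real and follows from the documents alone. Protocol 10.2.4.3 requires a fall of 34 points where Protocol 9.1.3.2, SAP 4.3.4.2 and SAP 7.9.3 use 3. The figure is 53% of a 64-point scale and cannot be reached from a baseline below 34. It is more than clerical, because it determines who counts as deteriorated.

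The effect is confined to one descriptive exploratory summary. If the text were followed literally, the symptom component would be nearly empty: about 0-3% at a visit instead of 34-72%, given an assumed mean change of 0 to −6 and SD of 6 to 15. The primary and key secondary analyses are untouched, and so is the 3-point event threshold in SAP 7.9.3. That section's only fault here is the wrong direction in its censoring sentence. The conclusion also assumes that the printed page reads 34.

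**What to change.** 1. Check the original page of Protocol 10.2.4.3. If it reads 34, replace it with 3 points or more, in line with Protocol 9.1.3.2.
2. In SAP 7.9.2, either add the deterioration proportion with the 3-point threshold or state that it was dropped.
3. In SAP 7.9.3, change the censoring sentence so that it refers to a decrease of 3 points or more.
4. Leave the SAP 7.9.3 event as it is. In the reports, label the time-to-event analysis as symptom-only and the proportion as symptom-or-death, so that the two are not read as the same quantity.

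The cost is one figure in the protocol, one line in SAP 7.9.2, one word in SAP 7.9.3 and a label in the outputs. No new data are needed. The 3-point value is already the trial's stated criterion, so adopting it chooses no new threshold. Adding death to SAP 7.9.3 would be a different kind of change: a new event definition made after the subject-level unblinding that SAP 5.2.1 records following the 09MAR2021 PFS analysis.
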